## 6.4 Analysis of Efficacy

Efficacy analyses will be conducted on the FAS and RAS. The interpretation of results from statistical tests will be based on the FAS. The RAS will be used to assess the robustness of the results from the statistical tests based on the FAS. All randomized subjects will be analyzed according to the treatment to which they are randomized/assigned. Efficacy data from the China cohort will be analyzed separately.

Derived response based on central assessment supplemented by local assessment: response will be derived based on the definitions in Section 7.1.1 using centrally evaluated myeloblast counts from bone marrow aspirate or biopsy assessments whichever is present (if both are present, both must qualify for the criteria) and centrally evaluated hematology results including ANC, platelet count and blast count in peripheral blood. If neither central bone marrow aspirate nor biopsy is available at baseline assessment, then myeloblast counts from locally evaluated bone marrow aspirate/biopsy assessments (if both are present, both must qualify for the criteria) will be used for all timepoints of assessment. Missing hematology results will not be imputed.

Derived response will be considered as primary and investigator reported response will be considered as supportive.

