7.1.1.2 Myelodysplastic Syndrome Response Criteria

Response to treatment will be defined according to the modified International Working Group response criteria [Cheson et al, 2006] as outlined below.

- Complete Remission (CR)

For subjects to be classified as being in CR at a post-baseline visit, they must have all of the following maintained for a minimum of 4 weeks:

- Bone marrow evaluation: $\leq 5\%$ myeloblasts with normal maturation of all cell lines
- Peripheral blood evaluation:
 - Hemoglobin ≥ 11 g/dL
 - Platelets $\geq 100 \times 10^9/L$
 - Neutrophils $\geq 1.0 \times 10^9/L$
 - 0% blasts in blood

- Partial Remission (PR)

For subjects to be classified as being in PR at a post-baseline visit, they must have all CR criteria if abnormal before treatment except the following for a minimum of 4 weeks:

- Bone marrow blasts decreased by $\geq 50\%$ over pretreatment but still $> 5\%$
- Cellularity and morphology not relevant

- Marrow CR

For subjects to be classified as being in marrow CR at a post-baseline visit, they must have all of the following for a minimum of 4 weeks:

- Bone marrow: $\leq 5\%$ myeloblasts and decrease by $\geq 50\%$ over pretreatment
 - Peripheral blood: if HI responses, they will be noted in addition to marrow CR

- Hematologic Improvement (HI)

Requires 1 measurement of the following maintained for at least 8 weeks without ongoing cytotoxic therapy:

- HI – erythroid:

- Hemoglobin increase of ≥ 1.5 g/dL
or
- For RBC transfusions performed for hemoglobin ≤ 9.0 g/dL: reduction in RBC units transfused in 8 weeks by ≥ 4 units compared to the number of units transfused in the 8 weeks prior to treatment
- HI – platelets:
 - For pre-treatment platelet count of $>20 \times 10^9/L$ platelet, absolute increase of $\geq 30 \times 10^9/L$
 - For pre-treatment platelet count of $< 20 \times 10^9/L$, platelet absolute increase of $> 20 \times 10^9/L$ and $\geq 100\%$ increase from pre-treatment level
- HI – neutrophils:
 - Neutrophil count increase of $\geq 100\%$ from pre-treatment level and an absolute increase of $> 0.5 \times 10^9/L$

- **Relapse after CR or PR**
Requires at least 1 of the following:
 - Return to pre-treatment bone marrow blast percentage
 - Decrement of $\geq 50\%$ from maximum response levels in granulocytes or platelets
 - Transfusion dependence or hemoglobin level ≥ 1.5 g/dL lower than prior to therapy

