- Partial Remission (PR): For subjects to be classified as being in PR at a post-baseline visit, they must have bone marrow regenerating normal hematopoietic cells with evidence of peripheral recovery with no (or only a few regenerating) circulating blasts and with a decrease of at least 50% in the percentage of blasts in the bone marrow aspirate with the total marrow blasts between 5% and 25%. A value of less than or equal to 5% blasts is also considered a PR if Auer rods are present. There should be no evidence of extramedullary leukemia.
- Not Evaluable (NE)/No Response (NR): In the situation where no bone marrow assessments are performed or myeloblast value is missing, blast value from peripheral blood is missing or  $\leq 2\%$ , and extramedullary leukemia is missing or not present, the response will be

classified as NE. In any case response cannot be categorized as CR, CRp, CRi, PR or NE, it will be categorized as NR.

A complete response classification schema is presented in [Table 1](#), below.

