**Table 1 Response Classification Schema for AML**

Myeloblast in Bone Marrow Aspirate/Biopsy	Blast in Peripheral Blood	Extramedullary Leukemia	Auer Rod	RBC Transfusion	Platelet Transfusion	ANC	Platelet	Response
<5%	Missing or <=2%	Absent/Missing	Absent/Missing	No	No	$\geq 1 \times 10^9/L$	$\geq 100 \times 10^9/L$	CR
<5%	Missing or <=2%	Absent/Missing	Absent/Missing	No	No	$\geq 1 \times 10^9/L$	< 100 $\times 10^9/L$	CR p
<5%	Missing or <=2%	Absent/Missing	-	-	-	$\geq 0.5 \times 10^9/L$	$\geq 50 \times 10^9/L$	CR h
<5%	Missing or <=2%	Absent/Missing	Absent/Missing	-	-	-	-	CR i
>=5% - <=25% and >=50% decrease from baseline	Missing or <=2%	Absent/Missing	-	-	-	-	-	PR
<5%	Missing or <=2%	Absent/Missing	Present	-	-	-	-	PR
Missing	Missing or <=2%	Absent/Missing	-	-	-	-	-	NE
Any case that cannot be categorized as CR, CR p , CR h , CR i , PR, or NE								NR

- Relapse
  - Relapse after CR, CRh, CRp or CRI is defined as a reappearance of leukemic blasts in the peripheral blood (> 2%) or  $\geq 5\%$  blasts in the bone marrow aspirate not attributable to any other cause or reappearance or new appearance of extramedullary leukemia.
  - Relapse after PR is similarly defined with reappearance of >2% of peripheral blasts and an increase in the percentage of blasts in the bone marrow aspirate to > 25% not attributable to any other cause or reappearance or new appearance of extramedullary leukemia.
- Best Response
  - Best response is defined as the best measured response to treatment for all visits (in the order of CR, CRp, CRI, PR, NR and NE) post-baseline. Subjects who achieve the best response of CR, CRp, CRI or PR will be classified as responders. Subjects who do not achieve at least a best response of PR will be considered non-responders.
- MDS
  - Complete Remission (CR): For subjects to be classified as being in CR at a post-baseline visit, they must have all of the following maintained for a minimum of 4 weeks:
    - Bone marrow evaluation:  $\leq 5\%$  myeloblasts with normal maturation of all cell lines
    - Peripheral blood evaluation:
      - Hemoglobin  $\geq 11$  g/dL
      - Platelets  $\geq 100 \times 10^9$  /L
      - Neutrophils  $\geq 1.0 \times 10^9$ /L
      - 0% blasts in blood
  - Partial Remission (PR): For subjects to be classified as being in PR at a post-baseline visit, they must have all CR criteria if abnormal before treatment except the following for a minimum of 4 weeks:

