    - Bone marrow blasts decreased by  $\geq 50\%$  over pretreatment but still  $> 5\%$
    - Cellularity and morphology not relevant
  - Marrow CR: For subjects to be classified as being in marrow CR at a post-baseline visit, they must have all of the following for a minimum of 4 weeks:
    - Bone marrow:  $\leq 5\%$  myeloblasts and decrease by  $\geq 50\%$  over pretreatment
      - Peripheral blood: if HI responses, they will be noted in addition to marrow CR
  - Hematologic Improvement (HI): For subjects to be classified as having hematologic improvement (HI) at a post-baseline visit, they must have 1 measurement of the following, maintained for at least 8 weeks without ongoing cytotoxic therapy:
    - HI – erythroid:

- Hemoglobin increase of  $\geq 1.5$  g/dL or
- For RBC transfusions performed for hemoglobin  $\leq 9.0$  g/dL: reduction in RBC units transfused in 8 weeks by  $\geq 4$  units compared to the number of units transfused in the 8 weeks prior to treatment
- HI – platelets:
  - For pre-treatment platelet count of  $>20 \times 10^9$  /L platelet, absolute increase of  $\geq 30 \times 10^9$  /L
  - For pre-treatment platelet count of  $< 20 \times 10^9$  /L, platelet absolute increase of  $> 20 \times 10^9$  /L and  $\geq 100\%$  increase from pre-treatment level
- HI – neutrophils:
  - Neutrophil count increase of  $\geq 100\%$  from pre-treatment level and an absolute increase of  $> 0.5 \times 10^9$  /L
- Relapse after CR or PR: For subjects to be classified as relapsing after CR or PR requires at least one of:
  - Return to pre-treatment bone marrow blast percentage
  - Decrement of  $\geq 50\%$  from maximum response levels in granulocytes or platelets
  - Transfusion dependence or hemoglobin level  $\geq 1.5$  g/dL lower than prior to therapy
- Stable Disease (SD): For subjects to be classified as having Stable Disease (SD), they must fail to achieve at least PR but show no evidence of progression for  $>8$  weeks
- Progressive Disease (PD): For subjects to be classified as having Progressive Disease (PD), they must show blast level increases depending on prior levels as follows:
  - For patients with:
    - $<5\%$  blasts:  $\geq 50\%$  increase in blasts to  $> 5\%$  blasts
    - $5\%-10\%$  blasts:  $\geq 50\%$  increase to  $> 10\%$  blasts
    - $10\%-20\%$  blasts:  $\geq 50\%$  increase to  $> 20\%$  blasts
    - $20\%-30\%$  blasts:  $\geq 50\%$  increase to  $> 30\%$  blasts
  - Or any of the following:

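### Read literally, the SAP rule that aspirate and biopsy must both qualify leaves a CR-range/PR-range pair in no response category, which can drop responders from the AML best response rate and the MDS primary rate

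*SAP*

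**What the plan says.** SAP 6.4 (Analysis of Efficacy) derives response from centrally read myeloblast counts, taken from aspirate or biopsy, whichever exists. For visits with both it adds: "if both are present, both must qualify for the criteria". The same section gives this derivation priority: "Derived response will be considered as primary and investigator reported response will be considered as supportive".

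The marrow criteria are separate bands, not nested thresholds.

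- **AML (SAP 5.1.1 and Table 1).** CR, CRp and CRi need blasts below 5%. The main PR row reads ">=5% - <=25% and >=50% decrease from baseline". Low blasts count as PR only in one situation: "A value of less than or equal to 5% blasts is also considered a PR if Auer rods are present". The remainder is explicit: "In any case response cannot be categorized as CR, CRp, CRi, PR or NE, it will be categorized as NR".
- **MDS (Protocol 7.1.1.2, SAP 5.1.1).** CR and marrow CR need at most 5% blasts. PR needs at least a 50% reduction from pretreatment with a value still above 5%, plus the CR blood criteria (where abnormal before treatment), for at least 4 weeks.

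PR counts in the AML best response rate (SAP 5.1.5) and in the MDS primary rate (SAP 6.4.1). Protocol 7.1.2 requires an aspirate and prefers a biopsy, so paired specimens are expected.

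**The concern.** A two-specimen rule is normally a safeguard: remission is not credited when one specimen contradicts it. That works when the categories are nested. Here PR has a lower bound on blasts, so a specimen that looks better than PR fails PR. When one specimen is in the remission range and the other in the PR range, remission fails on the second and PR fails on the first. The visit is then left without a response category, although each specimen on its own shows a response.

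The result is also not monotone: a pair with more residual disease gets a better category. For MDS this touches the primary endpoint, which drives the futility stops and the final rule of at least 10 responses in 52. For AML it touches a secondary rate only.

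**Working it through.** **1. The plan's own figure.** Inputs for MDS, from Protocol 9.1 and 9.4.1.3: stages of 12, 20 and 20; stop at 0/12 or at most 4/32; success at 10 or more of 52; rates 0.25 and 0.12. With X ~ Bin(12, p), Y ~ Bin(20, p) and Z ~ Bin(20, p):

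P(success) = Σ over x ≥ 1 and x + y ≥ 5 of P(X = x) · P(Y = y) · P(Z ≥ 10 − x − y).

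At p = 0.25 this is 0.835 (stopped at stage 1: 0.75^12 = 0.032; at stage 2: 0.057). At p = 0.12 it is 0.078. The stated power of about 0.83 and the 0.10 type I error limit are reproduced.

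**2. Apply the rule.** Classify each specimen separately, then keep only the categories that both meet. The blast values and baselines are illustrative, with the same baseline for both specimens.

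| Case | First specimen | Second specimen | Shared category |
|---|---|---|---|
| AML 3% / 8%, baseline 40%, no Auer rods | CRc range | PR | none, so NR |
| AML 8% / 10%, baseline 40%, no Auer rods | PR | PR | PR |
| AML 3% / 8%, baseline 40%, Auer rods present | PR | PR | PR |
| MDS 4% / 7%, baseline 16%, blood and 4-week criteria met | CR / marrow CR | PR (7 ≤ 0.5 × 16 = 8) | none |
| MDS 7% / 7%, baseline 16%, blood and 4-week criteria met | PR | PR | PR |
| MDS 4% / 7%, baseline 16%, blood criteria not met | marrow CR | no response | none |

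Rows 1 and 2 show the reversal in AML, and rows 4 and 5 show it in MDS. In row 6 the second specimen shows no response, so exclusion is ordinary conservatism and no two-specimen responder is lost.

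**3. Endpoints touched.** A CR-range/PR-range pair is not CRc even if it is assigned PR, so the AML primary rate does not change through this gap. The AML best response rate and the MDS CR + BM CR + PR rate can change.

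**4. Sensitivity for MDS.** Let d be the assumed share of responders lost, applied to both design rates, so p becomes p(1 − d). For example, d = 5% gives 0.25 × 0.95 = 0.2375.

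| d (assumed) | Power | Type I error |
|---|---|---|
| 0 | 0.835 | 0.078 |
| 2% | 0.815 | 0.070 |
| 5% | 0.783 | 0.059 |
| 10% | 0.721 | 0.044 |
| 20% | 0.568 | 0.022 |

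**5. A single case.** One lost responder in 52 is 1/52 = 1.9 points. At the threshold it moves 10/52 (19.2%, 90% CI 10.8 to 30.4) to 9/52 (17.3%, 9.3 to 28.3), below the success rule.

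**The case against.** The strongest reply is that the SAP never says such a subject is a non-responder. Requiring both specimens to qualify can be read as assigning the lower category that both reach. That gives PR and loses nobody. This stands to the extent that a loss is not established. It does not close the gap: the SAP does not state that reading, PR is not written as at least PR, and the residual NR row gives a programmer following the text a definite and different answer.

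Three limits on reach also stand. Best response is taken over all post-baseline visits (SAP 5.1.5), so one discordant visit costs a responder only if no other visit qualifies. AML visits with Auer rods remain PR. MDS visits matter only when the PR blood and 4-week criteria are met.

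The AML PR text in SAP 5.1.1 words the decrease on the aspirate, while Table 1 refers to aspirate or biopsy. Judging PR on the aspirate alone would not rescue every pair: with aspirate 3% and biopsy 8%, CR still fails on the biopsy and PR on the aspirate.

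A reader might also infer that the rule delays relapse or progression, since one specimen would not be enough. The documents do not support this. The rule in SAP 6.4 governs how response is derived. AML relapse is defined on the aspirate, peripheral blasts or extramedullary disease, and MDS relapse and progression have non-marrow triggers. EFS, duration of response and PFS are presented in listings only (SAP 6.4.2.4 to 6.4.2.6).

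Finally, investigator-reported response is a planned supportive analysis and may reveal discordant cases, but it is not the primary one.

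**Conclusion.** The point holds as a defect in the stated rule. Applied literally, it gives a non-monotone result in the primary, derived response and can drop responders from the AML best response rate and the MDS primary rate.

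A reader might go further and infer a demonstrated downward bias or a known loss of power. The documents do not support that, because they give neither the share of visits with both specimens nor a discordance rate. The fall from 0.835 to 0.783 or 0.721 is what an assumed 5% or 10% subject-level loss would do. It also assumes that the stage decisions use derived response and that losses are proportional at both design rates. What can be said without those assumptions is that one lost MDS responder is enough to change the conclusion at the 10/52 boundary. AML CRc, and so the AML decision rule, is not affected.

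**What to change.** In SAP 6.4, add after the two-specimen rule: when aspirate and biopsy are both present, classify each against its own baseline using the same blood and other criteria, and assign the less favourable of the two response categories. A CR-range/PR-range pair is then PR if the other PR criteria are met, and CR stays as strict as now.

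Two details belong in the same edit. First, name PR explicitly for this pair, because SAP 5.1.5 ranks MDS PR above BM CR and the order alone could be read differently (the MDS primary rate is the same either way). Second, say which baseline applies when a specimen type has none.

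Taking the higher blast percentage at each visit looks simpler, but it leaves open which baseline the 50% decrease is measured from.

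The cost is a short SAP edit and a small programming change, with no new data. Relapse and progression definitions need no change for this point.

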7.2.2 Laboratory Assessments

- See [Appendix [12.7](#) Laboratory Assessments] for the list of clinical laboratory tests to be performed and refer to the Schedules of Assessments [[Table 1](#) and [Table 2](#)] for timing and frequency.
- Laboratory samples will be analyzed by the institution's local laboratory. However, ONLY local sample results must be submitted for centralized data entry. Refer to the laboratory manual for additional information.
- Additional laboratory tests should be performed according to institutional standard of care.
- Local testing of bone marrow aspirate and/or biopsy will be reported in the eCRF; however, samples must also be submitted to a central laboratory for analysis. Refer to the laboratory manual for additional information.
- The investigator or subinvestigator must review the laboratory report and document this review.
- Clinical significance of out-of-range laboratory findings is to be determined and documented by the investigator or subinvestigator who is a qualified physician.

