Coagulation Profile (PT/INR, D-dimer, fibrinogen)	Except for IP administration days, collection of samples at local facility acceptable if results can be made available to investigative site	X ^a	X	X	X	X	X ^a	X	X	X	X ^a	X	X ^a	X	X ^k	Reference Table 15 : Alternative Schedule of Post-Treatment Period Assessments in Response to a Crisis			
Bone Marrow Aspiration and/or Biopsy ^e	May be obtained at a delayed time point when subject can visit the site and local BM collection is option to collect this data						X ^{a,e}					X ^{a,e}		X ^{a,e}	X ^e				
Blood Sample for Disease Assessment ^f	Except for IP administration days, may be obtained locally and results submitted to PI						X					X		X	X				

Table continued on next page

Assessments	Alternative Approach(es)	Treatment Period														EoT ^j	Post-Treatment Period		Survival Follow-up Period
		Cycle 1				Cycle 2				Cycles 3 – 4 ^m		Cycles 5 – 6 ⁿ		Obs Period 1	Obs Period 2				
Visit Days		D1	D2	D8	D15	D22	D1	D2	D8	D15	D22	D1	D15	D1	D15	Every 2 weeks for up to 12 weeks or until 1 post-treatment discontinuation criterion is met	Every 4 weeks or until 1 post-treatment discontinuation criterion is met	Every 3 months	
Window(days)		0	± 1	± 1	± 1	+ 3	0	± 1	± 1	± 1	+ 3	± 1	+ 3	± 1	+ 7			± 3	
AE/SAE Assessment	Completion by phone contact allowed for non-dosing visits with further assessment at local clinic if needed.																		
Pharmacokinetic: Blood Sample for Cell Kinetics	None	See Table 5 for detailed sample time points																	
PGx	None	X ^g															Reference Table 15: Alternative Schedule of Post-Treatment Period Assessments in Response to a Crisis		
Blood Sample for WT1 Expression	None	X ^a				X ^a					X ^a		X ^a		X ^k				
Blood Sample for Mutational Profiling	None	X ^a													X ^k				
Blood Sample for Immune Response Biomarker (ELISpot)	None	X ^a		X	X		X ^a		X	X		X ^a	X	X ^a	X	X ^k			
Buccal Swab for HLA Typing	None	X ^a																	
Blood Sample for Immune Response Biomarker (Tetramer)	None	X ^a			X		X ^a			X		X ^a	X	X ^a	X	X ^k			
Table continued on next page																			

Assessments	Alternative Approach(es)	Treatment Period														EoT ^j	Post-Treatment Period		Survival Follow-up Period
		Cycle 1				Cycle 2				Cycles 3 – 4 ^m		Cycles 5 – 6 ⁿ		Obs Period 1	Obs Period 2				

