Assessments	Alternate Approach(es)	Post-Treatment Period						Observation Period 2 Until 1 post-treatment discontinuation criterion is met	
		Observation Period 1 12 weeks or until 1 post-treatment discontinuation criterion is met							
		2	4	6	8	10	12		
Visit Week								Monthly Safety Assessment Visit	Assessment Visit Every 3 months
Window (days)		± 3	± 3	± 3	± 3	± 3	± 3	± 3	± 3
Physical Examination ^a	Can be obtained at local facility and results submitted to PI	X	X	X	X	X	X	X	X
Disease Assessment	Except for IP administration days, assessment can be performed locally and results submitted to PI	X	X	X	X	X	X	X	X
Vital Signs	Exams can be performed at a local clinic per SOC and results submitted to PI for evaluation	X	X	X	X	X	X	X	X
ECOG Performance	Can be completed by phone contact	X	X	X	X	X	X	X	X
Concomitant Medications ⁱ	Can be completed by phone contact	X	X	X	X	X	X	X	X
12-Lead ECG ^b	Except for IP administration days, assessment may be performed, as possible, at a local clinic and results submitted to PI. If cannot be performed, Astellas medical monitor to assess for study continuation.	X	X	X	X	X	X	X	X
Clinical Laboratory Tests (chemistry, hematology, coagulation, urinalysis) ^g	Collection of samples at local facility acceptable if results can be made available to investigative site	X	X	X	X	X	X	X	X

Table continued on next page

Assessments	Alternate Approach(es)	Post-Treatment Period						
		Observation Period 1						Observation Period 2
		12 weeks or until 1 post-treatment discontinuation criterion is met						Until 1 post-treatment discontinuation criterion is met
Visit Week		2	4	6	8	10	12	Monthly Safety Assessment Visit
Window (days)		± 3	± 3	± 3	± 3	± 3	± 3	± 3
Pregnancy Test for WOCBP	Test may be performed at local clinical and result submitted to PI	X	X	X	X	X	X	X
Bone Marrow Aspiration and/or Biopsy ^c	Except for IP administration days, may be obtained locally and results submitted to PI						X ^h	X
Blood Sample for Disease Assessment ^d	Except for IP administration days, may be obtained locally and results submitted to PI		X		X			X
AE/SAE Assessment	Completed by phone contact allowed with further assessment at local clinic if needed	X	X	X	X	X	X	X
Pharmacokinetic: Blood Sample for Cell Kinetics	None	See Table 5 for detailed sample time points						
Blood Sample for WT1 Expression	None		X		X		X ^j	X ^f
Blood Sample for Immune Response Biomarker (ELISpot)	None		X		X		X ^j	X ^e

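### The derived primary response has no fallback to the recorded local marrow count when a post-baseline central read is missing, so a remission can go uncounted

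*SAP*

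**What the plan says.** SAP 6.4 (Analysis of Efficacy) sets the order of evidence: "Derived response will be considered as primary and investigator reported response will be considered as supportive". The derived response is built "using centrally evaluated myeloblast counts from bone marrow aspirate or biopsy assessments whichever is present". Local marrow counts enter on one condition: "If neither central bone marrow aspirate nor biopsy is available at baseline assessment, then myeloblast counts from locally evaluated bone marrow" samples take over, and these "will be used for all timepoints of assessment. Missing hematology results will not be imputed". Nothing is said about a subject who has a central baseline but lacks a central count later.

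SAP 5.1.1 deals with a missing count in AML. "In the situation where no bone marrow assessments are performed or myeloblast value is missing", with peripheral blasts missing or at most 2% and extramedullary disease missing or absent, the visit is classed NE (also in SAP Table 1). Best response is taken over all post-baseline visits, and a subject who does not reach at least PR is a non-responder. The MDS ranking in SAP 5.1.5 (CR, PR, BM CR, HI, SD, PD) has no NE class. The primary rates divide by all subjects in the analysis population, and the primary set for efficacy is the FAS (SAP 4.1, 6.4.1).

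The local result is collected. Protocol 7.2.2 states: "Local testing of bone marrow aspirate and/or biopsy will be reported in the eCRF", and it also requires central submission. Protocol Table 12 likewise has local marrow blast and cell counts entered in the eCRF.

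**The concern.** The derivation is described as central with local support, yet the support stops at baseline. One missing central baseline makes local counts valid as primary evidence at every later visit. One missing later central read leaves the local count for that same visit unused, although it is in the database.

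For the AML primary endpoint this is hard to justify. CR, CRp and CRi all use an absolute marrow limit of under 5% blasts, so no baseline count is needed. SAP Table 1 also lets missing peripheral blasts, Auer rod or extramedullary data pass as compatible with remission, while a marrow count that was recorded is set aside.

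At stake is the primary rate in each disease. A responder whose only qualifying marrow lacks a central read stays in the denominator and leaves the numerator. The success rules are counts, at least 12 of 52 in AML and 10 of 52 in MDS, so an arm that lands on the threshold could turn on one such subject.

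**Working it through.** **Inputs.** Target and null rates: AML 0.30 and 0.15, MDS 0.25 and 0.12 (Protocol 9.1, SAP 3). Stages of 12, 20 and 20 subjects; stop at ≤1/12 and ≤5/32 in AML, ≤0/12 and ≤4/32 in MDS; success at ≥12/52 and ≥10/52 (Protocol 9.4.1.3). Stated power is about 0.83 with type I error held at 0.10.

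**Formula.** With b(n,x,p) the binomial probability, s1 and s2 the stopping limits and r the success count:

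Power(p) = Σ b(12,x,p) · b(20,y,p) · P[Bin(20,p) ≥ r − x − y], summed over x > s1 and x + y > s2.

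**Step 1: reproduce the plan's figure.** AML: power 0.829, type I error 0.067. MDS: power 0.835, type I error 0.078. Both agree with 0.83 and with an error below 0.10. (SAP 6.7 prints ≤6/32 as the second AML limit; that gives 0.801. The two documents need reconciling on that separate point, and the Protocol limit is used here.)

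**Step 2: model the loss.** Let m be the share of true responders who lose every qualifying central read. The observable rate is p(1 − m). Neither document gives m; the values below are assumptions.

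| m | AML rate | AML power | MDS rate | MDS power |
|---|---|---|---|---|
| 0 | 0.300 | 0.829 | 0.2500 | 0.835 |
| 1% | 0.297 | 0.819 | 0.2475 | 0.825 |
| 5% | 0.285 | 0.774 | 0.2375 | 0.783 |
| 10% | 0.270 | 0.708 | 0.2250 | 0.721 |

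At m = 10%, the chance of stopping for futility by 32 subjects at the target rate rises from 0.113 to 0.179 in AML and from 0.088 to 0.146 in MDS. At the null rate, type I error falls from 0.067 to 0.034 in AML and from 0.078 to 0.044 in MDS.

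**Step 3: relate m to a per-visit missing rate.** These are different quantities. In AML, if a responder has k qualifying visits and each central read is missing independently with probability q, then m = q^k. With q = 10%, m is 10% for one visit, 0.10² = 1% for two and 0.10³ = 0.1% for three. For MDS, CR, PR and marrow CR must hold for at least 4 weeks. If that is shown by two marrows, missing either one may lose the response, so extra visits protect less. The documents do not say whether a second marrow is required.

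**The case against.** The strongest case is that missing central reads should be uncommon and that the rule has a purpose.

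- **Central submission is mandatory.** A reader might infer from Protocol 12.9 that crisis-time marrows have only a local read, because Table 14 says "local BM collection is option to collect this data" and Table 15 says "Except for IP administration days, may be obtained locally and results submitted to PI". That inference fails. The footnotes to both marrow rows (e in Table 14, c in Table 15) still require submission to a central laboratory. Local collection is not a local read. What remains is samples that are lost or unreadable.
- **Poor aspirates have a backup.** An inadequate aspirate makes biopsy mandatory, and the SAP accepts either specimen. This stands and narrows the gap further.
- **Several visits can qualify.** Phase 2 marrows are scheduled on day 1 of cycle 2 and later cycles, at end of treatment (unless a recent sample exists), and in observation. This stands for lasting AML responses. It helps less for a short remission seen at one visit.
- **One source per subject.** MDS PR and marrow CR need a fall of at least 50% from pretreatment, and AML PR needs one in its main form. Mixing a central baseline with a local follow-up count would add reader differences to that comparison. This is a fair reason for those criteria. It does not apply to AML CRc.
- **Local reads in an open-label trial.** Letting them into the primary endpoint has a cost. The SAP already accepts that cost for subjects with no central baseline.
- **The remission may appear elsewhere.** Investigator-reported response is pre-specified as supportive, so a remission documented only locally can still be seen there. It does not drive the primary result.
- **The error is conservative.** It cannot create a false efficacy claim. This stands.

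**Conclusion.** The gap is real on the text of SAP 6.4. With a central baseline present and a later central read missing, the local count in the eCRF is not used. The AML visit is NE. The MDS visit has no defined class but cannot count as CR, BM CR or PR. The subject is an FAS non-responder only if no other visit qualifies. The effect on the primary rate is downward and lowers type I error.

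A reader might go further and conclude that the stated power of 0.83 is lost. The documents do not support that, because they give no missing-read rate. Over the assumed range of 1% to 10% of true responders losing every qualifying read, power is 0.819 to 0.708 in AML and 0.825 to 0.721 in MDS. The low end costs about one percentage point. These figures also assume that the BOP2 boundaries are applied to the derived response. Neither Protocol 9.4.1.3 nor SAP 6.7 says whether they use derived or investigator-reported response.

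This is a should-fix.

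**What to change.** In SAP 6.4, before database lock:

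1. **AML CRc.** At any post-baseline visit with no central aspirate or biopsy count, use the local myeloblast count from that visit for the criteria with the absolute limit of under 5%. Report the central-only derivation as a sensitivity analysis, with the number of substituted visits.
2. **Criteria needing a fall from baseline (AML PR, MDS PR, marrow CR).** Keep one source per comparison. Either use a local post-baseline count only against the local baseline count, or keep central-only as primary and pre-specify local substitution as a sensitivity analysis.
3. **MDS classification.** State how an MDS visit with no usable marrow count is classed.

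The cost is SAP wording and programming, using data the Protocol already collects. The downside is that a few local reads from an open-label trial enter the primary analysis, as the SAP already allows when the central baseline is missing. The central-only sensitivity analysis keeps the strict result visible.
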